5.6 Methods to Manage Incomplete or Missing Data

Unless otherwise specified, all data will be evaluated as observed, and no imputation method for missing values will be used.

5.6.1 Handling of Incomplete or Missing Dates

Any imputations on incomplete or missing dates will occur at the analysis dataset level. Imputed dates will be presented in all data listings.

5.6.2 AE Dates

AE Onset Date:

- If the onset date is completely missing:
 - If the date of study drug infusion is earlier than AE stop date, then the onset date will be assigned as the date of study drug infusion.

- If the date of study drug infusion is after the AE stop date then the AE onset date will be imputed as the earliest of complete AE stop date or informed consent date.
- If year is present and month and day are missing or year and day are present and month is missing:
 - If year = year of first dose, then set month and day to month and day of study drug infusion.
 - If year < year of first dose, then set month and day to December 31.
 - If year > year of first dose, then set month and day to January 1.
- If month and year are present and day is missing:
 - If year = year of study drug infusion and month = month of study drug infusion, then set day to day of study drug infusion.
 - If year = year of study drug infusion and month < month of study drug infusion, then set day to last day of month.
 - If year < year of study drug infusion, then set day to last day of month.
 - If year > year of study drug infusion, then set day to first day of month.

AE Stop Date:

- If the AE stop date is completely missing (not an ongoing AE) and AE onset date is complete, then the stop date will be imputed as the latest of the subject withdrawal/ completion date, death date, or AE onset date.
- If year is present and month and day are missing or year and day are present and month is missing, set end month and day to December 31.
- If month and year are present and day is missing, set the day to last day of the month.

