8.4.6 Adverse Events

AE collection will begin from time of informed consent and continue through the Week 112 visit. AEs will be documented at each clinic visit but can be collected at any time. Any AE that meets the definition of a Serious Adverse Event (SAE) will also be reported on a separate form to the Sponsor.

See Section 8.5 for information regarding AE collection and data handling.

Note: Any finding assessed by the investigator to be associated with the underlying AML, unless judged by the investigator to be more severe than expected for the subject's condition, will not be reported as an AE.

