6.5.1 Adverse Events

An AE is considered a treatment emergent adverse event (TEAE) if the event started or worsened during the safety reporting period as defined in Section 5.4.

All analyses will be based on TEAE unless otherwise specified. The AE listings will include all AEs (whether treatment-emergent or not).

AEs will be coded using the current version (as of study start) of MedDRA. Severity of AEs will be assessed by the Investigator using the National Cancer Institute (NCI) Common Terminology Criteria for Adverse Events (CTCAE), Version 5.0 toxicity grading criteria except CRS and ICANS, which will be graded by the Investigator according to the ASTCT criteria (1).

An event will be considered treatment related if the investigator considered the event related to the study drug, ie, relationship to NTLA-5001 = “Possible” or “Probable”, or if relationship is missing.

For summaries by System Organ Class (SOC) and preferred term (PT), each subject will be counted once per SOC and once per PT. In the summary of TEAEs by toxicity grade, subjects will be counted once at the highest severity reported at each level of summarization.

A high-level summary of AEs will include the number and percent of subjects with:

- Any TEAEs
- DLTs
- Treatment-related TEAEs
- Serious TEAEs
- Treatment-related serious TEAEs
- Grade ≥ 3 TEAEs
- Grade 3
- Grade 4
- Grade 5
- Treatment-related Grade ≥ 3 TEAEs
- Grade 3
- Grade 4
- Grade 5
- TEAEs leading to study drug infusion interruption
- Treatment-related TEAEs leading to study drug infusion interruption
- TEAEs leading to study drug infusion discontinuation
- Treatment-related TEAEs leading to study drug infusion discontinuation
- Treatment emergent AEs of special interest (AESIs)
- Treatment-related treatment emergent AESIs
- TEAEs leading to death
- Treatment-related TEAEs leading to death

The AESIs are defined in Section 8.5 in the protocol and will be summarized based on the data collected on the “Adverse Events” eCRF.

Adverse Events by Preferred Term

The following summaries will be provided by preferred term only by decreasing frequency.

- TEAEs by PT (all causality)
- Serious TEAEs by PT (all causality)
- Non-serious TEAEs by PT (all causality)

All AE data will be presented in a data listing.

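### Two partial-date rules in SAP 5.6.2 set AE onset to the infusion date without checking the stop date, so an event known to have ended before infusion is counted as treatment-emergent

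*SAP*

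**What the plan says.** SAP 5.6.2 treats AE onset dates in three groups.

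- **Onset completely missing.** The stop date is consulted. "If the date of study drug infusion is after the AE stop date then the AE onset date will be imputed as the earliest" of the complete stop date and the consent date, so the event stays before infusion.
- **Month missing (day known or not).** "If year = year of first dose, then set month and day to month and day of study drug infusion". There is no condition on the stop date.
- **Only the day missing.** For a matching year, the SAP continues: "month = month of study drug infusion, then set day to day of study drug infusion". Again there is no condition on the stop date.

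SAP 5.4 starts the safety reporting period on the infusion date. SAP 6.5.1 calls an AE treatment-emergent if "the event started or worsened during the safety reporting period as defined in Section 5.4". Protocol 9.4.2 also counts an onset on the dosing day. Protocol 8.4.6 states that "AE collection will begin from time of informed consent", so events that began and ended before infusion are in the database. SAP 5.6.1 puts imputed dates in all listings.

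**The concern.** Imputing towards treatment-emergence is a sensible default when timing is unknown. Here the timing that matters is known, because a recorded stop date before infusion shows that the event was over before NTLA-5001 was given. The rule overrides that fact and produces an onset later than the event's end. It is also inconsistent within the section: a record with no onset information keeps its pre-infusion status, while a record with the right year, or the right month and year, loses it.

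What is at stake is the TEAE flag, which feeds the high-level AE summary and the preferred-term tables in SAP 6.5.1. Leukapheresis, any bridging therapy and lymphodepletion on Day -5 to -3 all fall between consent and infusion, so AEs that end before infusion are to be expected.

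**Working it through.** **1. Following the rule through.** The documents give no figure to reproduce. The inputs are the onset and stop-date rules of SAP 5.6.2, the period in SAP 5.4 and the TEAE definition in SAP 6.5.1. For illustration, assume infusion on 20 Sep 2022.

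| Recorded onset | Recorded stop | Onset under SAP 5.6.2 | Onset minus stop | TEAE? | With stop-date check |
|---|---|---|---|---|---|
| 2022, month and day unknown | 5 Sep 2022 | 20 Sep 2022 | 15 days | Yes | 5 Sep, not a TEAE |
| 2022, month unknown, day 3 | 5 Sep 2022 | 20 Sep 2022 | 15 days | Yes | 5 Sep, not a TEAE |
| Sep 2022, day unknown | 18 Sep 2022 | 20 Sep 2022 | 2 days | Yes | 18 Sep, not a TEAE |
| Aug 2022, day unknown | 10 Aug 2022 | 31 Aug 2022 | 21 days | No | 10 Aug, not a TEAE |

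The first three rows are wrongly classed. In the fourth the TEAE flag is right, but the dates are still in an impossible order. For contrast, a completely missing onset with stop 5 Sep 2022 would be imputed no later than 5 Sep and would not be a TEAE.

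**2. Whether another section repairs it.** SAP 5.6.5 has a guard against negative durations, but the section deals with partial dates other than those already covered, and AE dates have their own section. Even if it were carried over, it only makes the two dates equal. Moving onset back to the stop date would cure the error; moving the stop date forward to infusion would keep the false TEAE.

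**3. How often an eligible record is caught.** The documents do not count partial dates, so this shows only what happens to a record that already has a partial onset and a pre-infusion stop. Assumptions: every infusion date in 2022 (365 dates), onset 1 to W days before infusion, duration d of 1 to 14 days, stop before infusion, all combinations weighted equally. The number of records per infusion date is the sum over d of (W − d + 1) = 14(W + 1) − 105.

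| W (days) | Records | Become TEAEs, month missing | Become TEAEs, only day missing | After the check |
|---|---|---|---|---|
| 33 | 371 × 365 = 135,415 | 94.5% | 35.1% | 0 |
| 60 | 749 × 365 = 273,385 | 90.8% | 17.4% | 0 |
| 90 | 1,169 × 365 = 426,685 | 86.7% | 11.1% | 0 |

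The month-missing branch catches nearly every such record, because onset and infusion usually share a year. The day-missing branch catches a minority, and fewer as the window lengthens.

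**4. Effect on a reported incidence.** SAP section 7 gives 2 treated subjects, which is the Safety Analysis Set denominator. One false TEAE in a subject with no other event in the category adds 1/2 = 50 percentage points. If that subject already has a genuine event in the category, the change is 0, because each subject is counted once.

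**The case against.** The strongest reply is that the practical effect is small. The error needs a partial onset in one of two branches together with a stop date known to precede infusion; partial onsets in an earlier month or year never reach the infusion date. No affected record is shown to exist. Only 2 subjects were treated, no hypothesis is tested, and the AE listings include all AEs whether treatment-emergent or not, so with the stop date displayed an onset after it should be easy to spot. All of this stands. It limits how often the rule matters and how far it could mislead, but it does not make the rule correct.

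A reader might go further and infer that the rule attributes bridging or lymphodepletion toxicity to NTLA-5001. The documents do not support that. A TEAE flag is about timing; attribution comes from the investigator's relationship assessment, and the preferred-term tables are for all causality.

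A reader might also infer that such events would usually enter the treatment-related rows, because SAP 6.5.1 counts an event as related "or if relationship is missing". Protocol 8.5.3 requires the investigator to provide causality and has a Not Related category for an improbable temporal relationship. An event so recorded stays unrelated, so a missing relationship is possible but not shown to be likely.

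**Conclusion.** The point holds as a defect in the rule: two branches of SAP 5.6.2 can override a recorded stop date, give an onset after the event's end and create a TEAE that the collected data contradict. This follows from the text alone. The percentages in the working rest on assumed windows and durations and say nothing about how many partial dates were collected.

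The effect is conditional. It is 50 percentage points in a category if the affected subject has no other event there, and nothing otherwise. It reaches a treatment-related count only if the relationship is missing or recorded as Possible or Probable.

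Two larger readings should be set aside. Scaling the effect to a cohort of 3 (1/3 = 33 points) or an expansion of 9 (1/9 = 11 points) does not apply, because this SAP reports 2 treated subjects. Nor is any effect on the DLT count shown: SAP 6.1 names DLT incidence as the dose-escalation primary endpoint, and DLTs are judged against specific toxicity criteria in Protocol 6.2.1.2, with cohort data reviewed after 28 days of observation.

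**What to change.** Add one sentence to SAP 5.6.2 that governs every partial-onset branch:

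> If the AE stop date, with a partial stop date taken at its latest possible day, is before the infusion date, onset is imputed no later than the stop date and the event is not flagged as a TEAE; otherwise the rules below apply.

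The SAP's own stop-date rules already place a partial stop at the end of the month or year, so the check acts only when the event certainly ended before infusion. The conservative default remains wherever the stop date is missing or does not settle the order. Covering every branch also corrects the impossible date order in the earlier-month case.

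The cost is that sentence and a few lines of code. The rule on missing relationship needs no separate change: analyses are based on TEAEs, so events that ended before infusion drop out once the check is in place.

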5.6.3 Exposure

No imputation will be done for the dosing date.

5.6.4 Date of Death

Missing or partial death dates will be imputed based on the last contact date:

- If the date is missing, it will be imputed as the day after the date of last contact.
- If the day or both day and month is missing, death will be imputed to the maximum of the full (non-imputed) day after the date of last contact and the following:
 - Missing day: 1st day of the month and year of death.
 - Missing day and month: January 1st of the year of death.

5.6.5 Other Missing or Partial Dates

Imputation methods for other partial dates are as follows:

- If the day of the month is missing for a start date used in a calculation, the 1st of the month will be used to replace the missing date.
- If both the day and month are missing, the first day of the year is used
- For stop dates, the last day of the month, or last day of the year is used if the day or day and month are missing, respectively

These rules are used unless the calculations result in negative time durations (e.g., date of resolution cannot be prior to date of onset). In such case, the resolution and onset dates will be the same and the duration will be set to 1 day.

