6.6 Concomitant Therapy

At the time of NTLA-5001 administration, tocilizumab (8 mg/kg IV) must be available on site.

After the Day 28 visit and assessments, AML therapy may be initiated for subjects not receiving benefit at the discretion of the investigator.

Any medication or vaccine (including over the counter or prescription medicines, vitamins, and/or herbal supplements) that the subject is receiving at the time of enrollment or receives during the study must be recorded along with:

- reason for use
- dates of administration including start and end dates
- dosage information including dose and frequency

The Medical Monitor should be contacted if there are any questions regarding concomitant or prior therapy.

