3 STATISTICAL HYPOTHESES AND SAMPLE SIZE DETERMINATION

3.1 Statistical Hypotheses

There is no statistical hypothesis for the study.

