3.2 Sample Size Determination

No formal sample size calculation was performed for this study.

Dose escalation will consist of up to 3 dose escalation cohorts in each of 2 Arms. Each Arm 1 cohort will include up to 6 subjects. Each Arm 2 cohort will include 3 to 6 subjects. Therefore, up to 36 evaluable subjects are anticipated to be enrolled in this portion of the study.

Once a dose is identified for detailed safety assessment in an Arm, a safety expansion cohort will be opened for up to 9 additional subjects to be dosed at that dose level. Thus, up to a total of 18 subjects will be dosed in safety expansion cohorts across the 2 Arms.

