5.4 Safety Reporting Period

The safety reporting period is defined as the time from the date of NTLA-5001 infusion through the end of the study or (start date of new anticancer therapy – 1 day).

Note that the safety reporting period will be used for all safety analyses.

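### The SAP dates a partly known start of new anticancer therapy as early as possible, which can only shorten the TEAE window, and lets partly known AE stop dates fall after death

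*SAP*

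**What the plan says.** **End of the safety window.** SAP 5.4 runs the safety reporting period from infusion "through the end of the study or (start date of new anticancer therapy – 1 day", and this period governs every safety analysis. SAP 6.5.1 counts an AE as treatment-emergent if it began or worsened inside the period.

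**Partial start dates.** SAP 5.6 has separate rules for AE dates, dosing and death. New anticancer therapy is not among them, so SAP 5.6.5 applies: "If the day of the month is missing for a start date used in a calculation, the 1st of the month will be used". With day and month both missing, 1 January is used. The only override concerns negative durations, and no lower limit at infusion is set.

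**When new therapy may begin.** Protocol 6.6: "After the Day 28 visit and assessments, AML therapy may be initiated for subjects not receiving benefit".

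**Partial AE stop dates.** If only the year is usable, SAP 5.6.2 says to "set end month and day to December 31". If only the day is missing, month-end is used. Neither is limited by death. A wholly missing stop date, by contrast, is tied to study exit, death or AE onset, whichever is latest.

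**Listings.** SAP 5.6.1: "Imputed dates will be presented in all data listings". It mentions neither a flag nor display of the partial date as collected.

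**The concern.** Setting a start date to its earliest possible value is a common default. Here, however, the date closes an observation window, so the default works against safety reporting: events that truly began before new therapy can be classed as after it and lose TEAE status. Protocol 9.4.2 defines TEAEs with no end at new therapy. The SAP adds that end, so an imputed therapy date can now decide whether an event is counted. Starts soon after Day 28 are foreseeable, because that is when the protocol first allows them.

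The AE stop-date rule has a different defect. For a subject who died, knowing the year of resolution can give a less plausible date than knowing nothing, because only the wholly missing date refers to death.

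**Working it through.** The plan states no figure to reproduce, so the check is calendar arithmetic on the SAP's rules.

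**Inputs**
- Infusion is Day 0 (protocol 4.1). SAP 5.2 numbers the infusion date as Day 1, so add 1 to each day below for SAP numbering.
- Window end = start of new therapy − 1 day (SAP 5.4, taking the earlier of its two end points).
- DLT period: onset within 28 days of infusion (protocol 6.2.1.2).
- True therapy start on Day *t*. The values of *t* are assumptions; the documents give no therapy dates.

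**Direction.** Imputed start ≤ true start, so imputed window end ≤ true window end. The loss is largest when the true start is the last day of a 31-day month (30 days). For a year-only date, the imputed start can precede the true start by up to 364 days in a non-leap year; how much of the window this removes depends on the infusion date.

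**Example**
- Infusion on 20 April 2022, so Day 28 is 18 May.
- Therapy truly starts on 25 May (Day 35) and is recorded as May 2022.
- Imputed start: 1 May (Day 11). The window closes on 30 April (Day 10).
- True window end: 24 May (Day 34). Days lost: 34 − 10 = 24, namely Days 11 to 34.
- Of these, Days 11 to 28 lie in the DLT period: 28 − 10 = 18 days.

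**How special is the example?** The table gives the share of the 365 infusion dates in 2022, equally weighted, for which the window ends before Day 28.

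| True start (Day *t*) | Day missing | Day and month missing |
|---|---|---|
| 29 | 97% | 99.7% |
| 35 | 77% | 98% |
| 42 | 54% | 96% |
| 56 | 8% | 92% |
| 59 | 0% | 91.5% |
| 112 | 0% | 77% |
| 180 | 0% | 58% |

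The month-only cut-off follows directly. The earliest possible window end is *t* − 31, and *t* − 31 < 28 requires *t* < 59. For year-only dates the imputed window end often precedes infusion itself: 92% of infusion dates at *t* = 29 and 69% at *t* = 112.

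**AE stop dates.** Take a death on 10 June 2022 and an AE stop recorded only as 2022. The imputed stop is 31 December, and 20 + 31 + 31 + 30 + 31 + 30 + 31 = 204 days after death. Over all death dates in a non-leap year, the 31 December rule runs up to 364 days past death (mean 182) and the month-end rule up to 30 days (mean 14.7).

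**Effect of the proposed start rule on the example.** The latest date consistent with May 2022 is 31 May (Day 41), so the window ends on 30 May. No day before therapy is lost, and 30 − 24 = 6 days from the start of therapy onward are included.

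**The case against.** The strongest reply is that the consequences are limited, and most of it stands.

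- **DLTs.** A reader might infer that a DLT could be lost. The documents do not support this. DLTs are defined by onset after infusion, not by the TEAE window. SAP 6.1 marks them in the overall AE listing, and SAP 6.5.1 puts all AEs in that listing, treatment-emergent or not. What is exposed is the TEAE summaries and possibly the DLT row of the overview, since analyses are TEAE-based by default.
- **DLT duration limits.** A reader might infer that wrong stop dates undermine the 72-hour, 7-day or 28-day limits. Escalation rests on review by the sponsor and treating investigators (protocol 6.2.1.1). Nothing says that this review uses imputed SAP listings, and the SAP plans no AE duration output.
- **Unmarked dates.** It is tempting to say that listings will pass imputed dates off as collected. The SAP is silent on flags and on showing the partial date; silence is not a decision to omit them.
- **One-day window.** The fallback in SAP 5.6.5 is written about onset and resolution dates. Reading it as cutting the safety window to one day is an extension. The text simply does not say what happens when the imputed therapy start precedes infusion.
- **Data cutoff.** SAP 5.1.1 excludes data after the cutoff, so a missing cap there is arguable. It says nothing about death.
- **Likelihood.** Protocol 6.6 requires start and end dates for all medication, and no document shows a partial date.

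None of this changes the direction of the start-date rule or supplies a cap at death.

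**Conclusion.** The point holds as a defect in two stated rules, with limited consequences. A partly known therapy start can only shorten the TEAE window. It can close the window before Day 28 if the true start is before Day 59 (day missing), or over a much wider range (day and month missing). Partly known AE stop dates can be listed after death.

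This rests on SAP 5.6.5 governing new-therapy dates, on SAP 5.4 meaning the earlier of its two end points, and on a partial date occurring at all. SAP section 7 reports two treated subjects, so one affected subject would be 1/2 = 50% of the safety denominator; equally, both records can be checked by hand. No inference is at risk: "There is no statistical hypothesis for the study". In practice this is a minor matter, worth correcting because correction is cheap.

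**What to change.** Amend SAP 5.6 as follows.

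(a) For the therapy start that closes the safety period, impute the latest date consistent with the recorded parts, no later than death or last contact and never before infusion.

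(b) Cap imputed AE stop dates at the date of death, without contradicting a recorded month or year; if the recorded parts themselves fall after death, query the record. Do not cap at study exit: protocol 8.5.6 follows AEs after a subject discontinues, so a true stop date can be later than exit.

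(c) In listings, show the partial date as collected or flag the imputed one.

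The cost is a few sentences and a few lines of programming. Rule (a) can class some events after the start of new therapy as TEAEs. For month-only dates this adds at most 30 days (true start on the 1st, imputed to the 31st); for year-only dates the excess can be longer, up to death or last contact. That errs towards reporting more events.
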